Using a large sample, we will determine the psychometric properties of health questionnaires across levels of health literacy. Testing will be conducted in English and Spanish, across two modes of administration (paper-and-pencil vs. talking touchscreen). Each participant will have three visits (baseline, 3-month, and 6-month follow-up), described below, in order to determine changes in psychometric properties over time. We will use *differential item functioning* (DIF) and other psychometric analyses to identify questionnaire items with varying characteristics across levels of health literacy. Before the COVID-19 pandemic, our original plan was to recruit $N = 1216$ participants for in-person assessments. At the time of this plan our final N is 728 participants who have completed a health literacy assessment; some of these participants are missing data on subsequent questionnaires. In-person recruitment was put on hold during the COVID-19 pandemic; in order to adapt the the pandemic, a subset of participants ($N = 304$) was invited to a phone-based protocol that included data collection about the impact of COVID-19, vaccine confidence, and health-related quality-of-life (PROMIS-29 profile).

- **Develop alternative modes of test administration that can better accommodate people with low health literacy.** National statistics indicate that 14% of adults in the United States have below basic reading skills, and over 75 million Americans have below basic or basic health literacy skills.¹⁴ These data strongly indicate that many individuals seeking health care will have difficulties with written questionnaires, even those that have been carefully developed such as those in the NIH PROMIS. We will test an alternative mode of administration that has been specifically designed to aid people of low health literacy – a computer-assisted “talking” version that uses speech technology that participants can privately access as needed to have items and response options

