Each participant will be asked to complete a baseline assessment (Visit 1), three-month follow-up (Visit 2), and a six-month follow-up (Visit 3). Longitudinal data will be analyzed, within language and within mode of administration (paper-based vs. talking touchscreen), on a scale-by-scale basis using multiple-group factor analysis to compare in Mplus software (see Table 3 schematic below). All items will be treated as categorical indicators with response categories collapsed if there are fewer than five responses for a given response option.

Table 3: Schematic of multiple-group confirmatory factor analysis to be used on a scale-by-scale basis			
	Visit 1	Visit 2	Visit 3
Adequate health literacy	Factor loadings/ IRT parameters	Factor loadings/ IRT parameters	Factor loadings/ IRT parameters
Low health literacy	Factor loadings/ IRT parameters	Factor loadings/ IRT parameters	Factor loadings/ IRT parameters

We hypothesize that a metric invariable model will fit well for the talking touchscreen method. Acceptable fit will be defined as $CFI \geq .90$, $TLI \geq .90$, and $RMSEA \leq .10$. We hypothesize that unacceptable fit indices will be obtained for the paper-based testing. For descriptive statistics, we will report all fit indices produced by Mplus as well as factor loadings for each item. Longitudinal data will also be used to develop new longitudinal DIF tools in R, but these results will be considered exploratory until they can be tried and tested in other data sets.

Study Populations

The study population includes medical patients and community member, all might which complete questionnaires in other clinical and research contexts, ages 18 and older.

Study Variables

Demographics

All demographic variables are described in the protocol. We will report descriptive statistics of all demographics within language group as well as in total. We do not have specific hypotheses about demographics, but may conduct and report analyses of them, as well as presented additional analyses of demographics based on requests from manuscript reviewers.

Health literacy and numeracy

HealthLiTT and the NUMI will be used to determine health literacy groups using the above-described cutoffs. HealthLiTT is our main health literacy variable. All analyses of the NUMI are secondary.

Health questionnaires

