$$\text{item slope}_j = a_j + b1_j * \text{Health LiTT} + b2_j * \text{Administration Type} + b3_j * \text{Interaction}$$

where j is an index for the k items (8 items in this case).

We will use Mplus in conjunction with the aMNLFA²⁴ package of R. Following the MNLFA procedure outlined by Curran et al.,²⁵ we will test models allowing item parameters (intercept and slope) to vary as a function of hypothesized DIF variable, one item at a time, in order to arrive at a final model. We will use the final model to generate item characteristics curves (ICCs, which will show the estimated probabilities of endorsement for each item across different levels of meaning and purpose. Among non-invariant items, we will consider differences (due to DIF variables) in probability endorsement of 10% to be potentially meaningful scientifically. Using the final model, we will also plot meaning and purpose factor scores by healthy literacy and administration type to understand the relationship among these variables. For these analyses, we will use all available baseline data collected through March of 2020 ($N = 566$ English speakers).

Longitudinal analyses of Meaning and Purpose Predicting Quality of Life. In addition to examining DIF by health literacy in the NIH Toolbox Meaning and Purpose measure (as described above), cross-lagged panel analyses will be used to examine whether meaning and purpose predicts health-related quality of life (i.e., anxiety, depression, fatigue, pain intensity and interference, physical function, sleep disturbance, and disruption of social roles and activities) over time across the three study assessments. We will also identify covariates including sociodemographics associated with meaning and purpose (i.e., age, gender, financial strain, education, race/ethnicity, language). We hypothesize that greater meaning and purpose will prospectively predict greater quality of life at subsequent study assessments. We will only include participants who could have provided complete data before we ceased recruitment due to COVID-19. Thus, we will exclude participants who are 1) were enrolled on or after 16 September 2020, and 3) missing their 6-month assessment. In this way, data will not be systemically missing due to censoring from the COVID-19 pandemic (i.e., to be eligible, the person would have had sufficient time to complete all three assessments before the COVID-19 pandemic).

Exit Interview

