This analysis will have several limitations. 1. The sample may not be generalizable as it was restricted to urban and English- or Spanish-speaking participants who consented to participation in a research study. 2. This is a baseline analysis that does not take into the account the potential for changing views on vaccination in the setting of an ongoing pandemic and public health education campaigns. We plan longitudinal analyses in the future to address this limitation. 3. Although we have hypothesized a causal pathway that includes race/ethnicity and health literacy as a partial mediator, we are unable to evaluate alternative pathways for factors that were not measured as part of this study. 4. Mediator-outcome confounding or collider bias is a possibility in this analysis in reference to the variable, educational level, which is related to health literacy and potentially related to the outcome of vaccine confidence. 5. In addition, the possibility of measurement error in the assessment of health literacy not only affects the estimate of health literacy's relationship with vaccine confidence, but also the estimate of the relationship of race or ethnicity with VCI.

Despite these limitations, we feel this analysis adds to the available knowledge on vaccine confidence during the COVID-19 pandemic and opportunities to improve public uptake of vaccination through targeted campaigns and interventions.

Cognitive Correlates of Rumination

Version notes. This plan was added in Version 4.2, 02 June 2021. At the time of the plan, adjust MOCA-B scores had been examined for distributional characteristics and differential item functioning for depression items (DIF; i.e., different measurement properties for PHQ-9 and PROMIS Depression by high-low MOCA-B). Some other analyses of rumination and depression had also been carried out as described in the above section *Prediction of depression: Health literacy as a moderator of rumination, pain, fatigue, and sleep disturbance*.

Sample. The sample will contain all participants ($N = 478$) who completed cognitive measures (see below) recruited into the parent health literacy study before recruitment was stopped due to the COVID-19 pandemic (March 2021). The cognitive measures were administered at one of three time points in the study; corresponding rumination and PROMIS depression measures will be used from the same time point.

Overarching goal

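### The 16 September 2020 enrolment cut-off for the longitudinal Meaning and Purpose analysis is at least 247 days too late for the pre-pandemic completion it is meant to secure

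*SAP*

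**What the plan says.** The rule is in the SAP under Meaning and Purpose Analyses, in the paragraph on longitudinal analyses predicting quality of life. It opens with the aim: "We will only include participants who could have provided complete data before we ceased recruitment due to COVID-19". The exclusions are participants who "were enrolled on or after 16 September 2020, and 3) missing their 6-month assessment". The paragraph then gives the benefit claimed: "In this way, data will not be systemically missing due to censoring from the COVID-19 pandemic". A parenthesis explains that eligibility means "the person would have had sufficient time to complete all three assessments before the COVID-19 pandemic".

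Other statements bear on the dates:

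- SAP, Study Timepoints: visits are at baseline, three months and six months.
- SAP, Meaning and Purpose DIF analysis, immediately before the longitudinal paragraph: it uses "all available baseline data collected through March of 2020".
- SAP, Study Objectives: "In-person recruitment was put on hold during the COVID-19 pandemic", with no date.
- SAP, Cognitive Correlates of Rumination, Sample: "recruitment was stopped due to the COVID-19 pandemic (March 2021", the only dated recruitment stop in either document.
- Protocol, version date 13 July 2020: section 4.1 extends the follow-up time-frames for people enrolled during the pandemic and suspends outstanding in-person visits while a participant is in the phone protocol. Section 4.5 expects phone recruitment to start in July 2020.

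**The concern.** An enrolment cut-off meant to leave six months of undisturbed follow-up should lie six months before the disturbance. This one lies after it: the protocol in force two months earlier was already written around the pandemic.

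The date is a decision threshold, because it sets who enters the cross-lagged model. Visit spacing is central to that model. People admitted by the date alone may have had their three- or six-month visits delayed under the extended time-frames, or not at all, and the paragraph asserts that the rule prevents pandemic-related missingness. An analyst who applies the printed date and one who applies the stated purpose would use different eligibility rules and could obtain different samples. The DIF and mode-of-administration objectives are not affected.

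**Working it through.** **Inputs**

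- Printed cut-off: exclude enrolment on or after 16 September 2020 (SAP, longitudinal Meaning and Purpose paragraph).
- Time needed for three assessments: 6 months (SAP, Study Timepoints). No visit windows are given, so nominal timing is used.
- Latest documented date by which in-person visits were disrupted: 13 July 2020 (protocol version date, with sections 4.1 and 4.5).
- Dated recruitment stop: March 2021, day not given (SAP, Cognitive Correlates of Rumination).

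**Formula**

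Latest admissible cut-off = reference date − 6 months. Days too late = 16 September 2020 − latest admissible cut-off.

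**Step 1. Can the printed date be reproduced?** 16 September 2020 + 6 months = 16 March 2021. It therefore matches, to the month, a recruitment stop in March 2021. No reference date in 2020 produces it.

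**Step 2. Test against completion before the pandemic, using the most lenient reference date.**

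- 13 July 2020 − 6 months = 13 January 2020.
- 16 September 2020 − 13 January 2020 = 247 days (245 to 248 if six months is taken as 180 to 183 days).
- The cut-off itself falls 16 September 2020 − 13 July 2020 = 65 days after the protocol version date.
- Enrolment dates wrongly admitted on this reference: 13 January to 15 September 2020. Their six-month visits fall due from 13 July 2020 to 15 March 2021.

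**Step 3. Earlier interruption.** 13 July 2020 is the date of a document, not of an onset, so 247 days is a minimum. If visits were interrupted in March 2020 (assumed):

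| Assumed interruption | Latest cut-off | Printed date is late by |
|---|---|---|
| 1 March 2020 | 1 September 2019 | 381 days |
| 16 March 2020 | 16 September 2019 | 366 days |
| 31 March 2020 | 30 September 2019 | 352 days |

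The middle row is what a wrong year would look like: 16 September 2019 + 6 months = 16 March 2020, the month in which the neighbouring DIF analysis closes its baseline data. The documents do not confirm this.

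**The case against.** The strongest defence is that the date does fit a recruitment stop in March 2021, and the paragraph's opening sentence speaks of recruitment ceasing. On that reading the date was derived correctly, and the parenthesis is only a loose restatement. The fit is real. It does not rescue the parenthesis or the claim about pandemic censoring, because March 2021 is at least eight months after the pandemic had altered the visit schedule. The March 2021 stop may also be a year slip. The protocol's planned three years of recruitment from March 2018 also end in March 2021, but that is an anticipated timeline, not a stop caused by COVID-19.

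Second, 247 days rests on a protocol version date and is not a measure of people affected. In-person recruitment was on hold for some undated period, so part of the admitted window may contain no enrolments. That stands. It does not make the date harmless. Suppose the hold began in March 2020 and nobody enrolled afterwards. The criterion would then exclude no one enrolled before the hold, and would still admit people enrolled from about September 2019 onwards whose six-month visits fell due after the interruption.

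Third, the exclusion for a missing six-month assessment might be thought to do the work instead. If it is a separate ground, it removes people without that visit but keeps those who completed it late. If it must hold jointly with the date, it does less. The list runs from item 1 to item 3; an item 2 may have been lost from the text or misnumbered, so no conclusion is drawn from it.

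Finally, this may be a simple date slip in one secondary association analysis. That limits its importance, but an a priori eligibility date that contradicts its own rationale still needs correction.

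**Conclusion.** The concern holds. The printed cut-off is incompatible with completing all assessments before the pandemic. It is too late by at least 247 days, using the latest interruption date the documents support and nominal six-month follow-up. It is too late by 352 to 381 days if the interruption was in March 2020, which is an assumption. The date is compatible only with the recruitment-stop wording read with a March 2021 stop. A wrong year is plausible but unconfirmed. The number of participants affected cannot be derived, and the effect is confined to the longitudinal Meaning and Purpose analysis. It should be fixed before that analysis is run.

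**What to change.** 1. State one date on which the pandemic interrupted in-person visits, and distinguish it from any later formal stop of recruitment. Reconcile the longitudinal Meaning and Purpose paragraph and the Sample paragraph of Cognitive Correlates of Rumination to it.
2. Set the enrolment cut-off six months before the interruption date, not before a later formal stop. If the interruption was in March 2020, this falls in September 2019; the sponsor must supply the day.
3. If only the recruitment-stop test is intended, keep the date and remove both the pre-pandemic explanation and the claim that the sample is free of pandemic censoring.
4. Check the source for item 2 of the exclusion list, restore it or renumber, and say whether the exclusions apply separately or jointly.

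The cost is one or two dates and one or two sentences in the SAP. The longitudinal sample may become smaller.

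### The Meaning and Purpose longitudinal analysis excludes anyone without a 6-month visit, a criterion that its own rationale (time to finish before the pandemic) does not support

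*SAP*

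**What the plan says.** The text is in the SAP under *Longitudinal analyses of Meaning and Purpose Predicting Quality of Life*. There, "cross-lagged panel analyses will be used to examine whether meaning and purpose predicts health-related quality of life" across the three visits.

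The sample is set in three consecutive sentences:

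- **Rule:** "We will only include participants who could have provided complete data before we ceased recruitment due to COVID-19".
- **Exclusions, presented as following from the rule:** item 1 covers people who "were enrolled on or after 16 September 2020"; the list then runs "and 3) missing their 6-month assessment". In the available text there is no item 2.
- **Purpose:** "data will not be systemically missing due to censoring from the COVID-19 pandemic", explained as "to be eligible, the person would have had sufficient time to complete all three assessments before the COVID-19 pandemic".

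No missing-data method is stated for this model. The full-information statement in the SAP's *Missing data* section is about the IRT models used for DIF. Listwise deletion is specified for the regressions that predict depression. Imputation is not foreseen.

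**The concern.** The rule and the purpose are both about opportunity: did the person have time to finish before the pandemic? The last exclusion is about what happened: was the 6-month visit done? It carries no condition on the reason or on the time available.

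Someone who enrolled early, attended baseline and month 3 and then stopped coming is ordinary attrition, not pandemic censoring, yet is removed. The baseline to month-3 paths are then estimated only in people who went on to return at month 6. If returning depends on month-3 quality of life, those paths are selected on their own dependent variable. Usable baseline and month-3 records are lost in any case, and a full-information estimator cannot recover people whom an eligibility rule has taken out.

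**Working it through.** The SAP gives no sample size, power or retention figure for this analysis, so there is no sponsor figure to reproduce.

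**1. The two readings of the list, tested on two people.** Participant A enrolled in 2018 (protocol 4.5 anticipates recruitment from March 2018), attended baseline and month 3, and missed month 6. Participant B enrolled after the cut-off and has a 6-month visit.

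| | A | B |
|---|---|---|
| Stated rationale | no ground to exclude | must be out |
| Each item excludes on its own | out | out |
| Both items must hold | in | in |

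Neither reading matches the rationale in both cases. The numbered list favours the first.

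**2. The cut-off date.** 16 Sep 2020 + 6 months = 16 Mar 2021. 16 Sep 2019 + 6 months = 16 Mar 2020. The DIF analysis just above says "we will use all available baseline data collected through March of 2020", while the SAP section *Cognitive Correlates of Rumination* puts the recruitment stop at March 2021. If the stop was March 2020, the printed date removes nobody enrolled by then, and the 6-month criterion alone defines the sample.

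**3. Size, by simulation on assumed inputs** (2,000,000 records; Monte Carlo error about 0.4% of the path).

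- M1 and Q1 (meaning and purpose, quality of life at baseline): standard normal, correlation 0.5.
- Month 3: Q2 = 0.6·Q1 + 0.15·M1 + 0.7·e. The true cross-lagged path is 0.15.
- Return at month 6: logit P = a + g·z(Q2), with g = 0.5 (odds ×1.6 per SD) or g = 1.0 (odds ×2.7 per SD), and a set to give total drop-out d.
- Shrinkage = 1 − (completers' estimate)/0.15. Standard-error rise = SE in completers / SE in everyone with month-3 data − 1.

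| d | g | All drop-out after month 3: shrinkage, SE rise | Half before month 3, at random: shrinkage, SE rise |
|---|---|---|---|
| 20% | 0.5 | 1.8%, 10.7% | 1.1%, 5.5% |
| 20% | 1.0 | 5.6%, 8.4% | 3.8%, 4.0% |
| 30% | 0.5 | 1.9%, 18.0% | 1.9%, 9.3% |
| 30% | 1.0 | 7.3%, 14.9% | 5.5%, 7.2% |
| 40% | 0.5 | 2.5%, 27.5% | 2.3%, 14.2% |
| 40% | 1.0 | 8.2%, 23.5% | 7.1%, 11.6% |

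If drop-out is unrelated to outcome (g = 0), the path stays at 0.150 to 0.151. The SE rise is then 1/√(1 − d) − 1: 11.8% at d = 20% and 29.1% at d = 40%.

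For month 3 to month 6, I used M2 = 0.6·M1 + 0.15·Q1 + 0.7·e and Q3 = 0.6·Q2 + 0.15·M2 + 0.7·e. Completers give 0.150 to 0.151 in every row. Return depends on Q2, which is a predictor in that equation, so no bias is expected.

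With other coefficients (correlation 0.4, stability 0.5, residual SD 0.78) the most extreme row shrinks by 10.0%, so the top of the range depends on the inputs.

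**4. Records lost.** With the SAP's 728 participants as an upper reference only (before the date rule and other missing data): 728 × 0.8 = 582, 728 × 0.7 = 510, 728 × 0.6 = 437.

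**The case against.** - **The rule sets a necessary condition.** A reader might infer that the SAP promises to keep everyone who had time and then breaks that promise. It does not: the rule says who may be included, and a further completion criterion is logically compatible with it. What stands is that the SAP offers pandemic censoring as the only reason for the exclusions, and that reason does not justify removing an early enrollee who dropped out.
- **The sentence is garbled.** With a number missing and an ambiguous conjunction, early drop-outs may not be excluded at all. This is fair, and it limits certainty about which fault applies. The other reading still fails, because it keeps late enrollees.
- **The criterion does some of the intended work.** Protocol 4.1 gave participants active during the pandemic extended time for visits 2 and 3, and put outstanding in-person visits on hold during the phone protocol. Some missing 6-month visits are therefore pandemic losses. If the printed date stands and recruitment stopped in March 2020, this criterion is the only thing that removes such people. This stands, and it means the criterion should not be deleted without also settling the date.
- **The harm is modest and conditional.** This stands too. The modelled bias runs towards zero, against the sponsor's hypothesis, and depends on a link between drop-out and outcome that the documents do not report.

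**Conclusion.** The point holds. The 6-month criterion does not follow from the stated rationale, and neither reading of the list implements it. On the likelier reading, the baseline to month-3 paths are estimated in later returners only.

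The size is small to moderate: roughly 1% to 8% shrinkage of the baseline to month-3 cross-lagged path and roughly 4% to 29% on its standard error. This rests on assumed drop-out of 20% to 40%, an assumed gradient on month-3 quality of life, and the share of drop-out that comes before month 3. The loss of precision needs no outcome-related drop-out, only drop-outs who have month-3 data.

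A reader might go further and infer that the whole longitudinal analysis is biased, or that the study's main comparison is affected. The documents do not support either. Month-3 to month-6 paths are unbiased under this mechanism, and the randomised paper versus touchscreen comparison and the DIF analyses do not use this exclusion. It should be corrected, but it does not undermine the trial.

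**What to change.** Rewrite the sentence as a single repair:

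1. Reconcile the enrolment cut-off with the recruitment-stop dates given elsewhere in the SAP, so that it leaves time for all three visits before the pandemic. Restore or remove the missing item 2.
2. Delete the criterion on the missing 6-month assessment, so that the set is defined by enrolment date.
3. State that the cross-lagged model is fitted by full-information maximum likelihood, so that participants with baseline only, or baseline plus month 3, contribute.
4. Report the completers-only fit as a sensitivity analysis, with the number lost at each visit.

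The cost is a short text change and an estimator option. The price is reliance on a missing-at-random assumption. That differs from what completers-only regression needs and is not uniformly weaker: completers-only regression is valid when missingness depends only on that regression's predictors, even unobserved ones. Some participants near the cut-off may still have delayed visits under protocol 4.1, so the report should count them.
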